5.2.2.2 Summary Measures

The 3-by-2 Contingency table (see Section 5.2.2.1) will be presented.

5.2.2.3 Assumption Checks

A check of the expected numbers in the 3-by-2 Contingency table (see Section 5.2.2.1) will be done. If any of these numbers are less than 5, the non-parametric Newcombe Hybrid Score will be used to calculate the risk differences between the groups pairwise

5.2.2.4 Missing Data

All patients are followed-up for re-ruptures until 12 months. The participating hospitals are instructed to report any re-rupture (total or partial) detected during the follow up period directly to the principal investigator. This will secure that the chance of missing the count of any re-rupture is regarded as insignificant.

5.2.2.5 Sensitivity Analyses

No sensitivity analyses will be performed.

5.2.2.6 Subgroup Analyses

No subgroup analyses will be performed.

STATISTICAL ANALYSIS PLAN for the Achilles trial

5.2.3 Continuous Secondary Outcome: SF-36v2

5.2.3.1 Main Analysis

The outcome is the change in the SF-36 score from baseline to the 6-month and the 1-2-year visit. The two summary scores, PCS and MCS, as well as the sub-score PF will be considered. Thus, there are three SF-36-based secondary outcome variables. Note that the SF-36 scores will be standardized to the 1998 US population, as provided by the ProCore software by Qualitymetric (<https://www.optum.com/business/solutions/life-sciences/answer-research/patient-insights/sf-health-surveys.html>).

The analyses will be conducted in the FAS.

5.2.3.2 Summary Measures

The 6-month and 1-2-year visit estimated marginal mean change in SF-36 score from baseline will be reported for each treatment group, together with 95% confidence intervals.

5.2.3.3 Assumption Checks

Similar as for the primary endpoint.

5.2.3.4 Missing Data

Partially answered SF-36 questionnaires will be treated according to the SF-36v2 user's manual [13]. Note that the manual allows for a certain degree of missingness in a given questionnaire. If the manual deemed a questionnaire as not sufficiently answered, then the score value for the individual at the visit in question will be treated as a missing value, in the same manner as completely unanswered questionnaires.

Missing baseline SF-36 score data will be imputed using mean imputation (9). Missing values in follow-up SF-36 scores (at the 6-month and the 1-2 years visits) will be handled by the mixed modelling approach. However, individuals with no follow-up measurements will then be excluded from the analysis. If the proportion of patients that has no follow-up measurements is less than 5%, no action will be taken to include these in the analysis. If this proportion is larger than 5%, multiple imputation will be used to impute SF-36 scores for these individuals.

5.2.3.5 Sensitivity Analyses

No sensitivity analyses will be performed.

5.2.3.6 Subgroup Analyses

No subgroup analyses will be performed.

5.2.4 Continuous Secondary Outcome: Muscle lab measurements

The six muscle lab measurement variables will be analysed in the same way.

5.2.4.1 Main Analysis

There are three outcomes for each physical test:

- The difference between the 6-month and the 1-2 years test performance.
- The 6-month test performance.

STATISTICAL ANALYSIS PLAN for the Achilles trial

- The 1-2-year test performance.

Linear regression models will be fitted to each of these outcomes, for each physical test. The treatment variable will be adjusted by study centre (the stratification variable used in the randomization). Note that for each of the 6 physical tests at each visit, a test is also performed in the healthy foot. The ratio between the performance in the treated foot and the healthy foot, multiplied with 100, (the LSI) is also considered an outcome variable for each physical test.

The analyses will be conducted in the FAS.

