2.7 Timing of Outcome Assessments

For all clinically planned measures, visits should occur within a window of the scheduled visit. Visits outside visit window is regarded a protocol deviation. The target day and visits window are defined in the protocol as:

Visit Label	Target Day	Definition (Day window)
Diagnosis	-1	Prior to Day 0
V1. Baseline	Day 0 (Randomization)	Day 0
V2. Surgery/Casting	Day 1	< 8 days from injury
V2. 2 weeks	14 days from casting	Target day \pm 7 days
V3. 4 weeks	28 days from casting	Target day \pm 7 days
V4. 8 weeks	56 days from casting	Target day \pm 14 days
V5. 3 months	91 days from casting	Target day \pm 30 days
V6. 6 months	182 days from casting	Target day \pm 30 days
Last study visit*	364 days from casting	334 to 728

*The patients are physically tested by a physiotherapist at 1-2 years. Most often they are asked to complete the PROMs prior to the testing, either by link send by e-mail, on site on a tablet, or on paper when a tablet is not present or online. Some patients did not show up for the 1-2 years testing but did complete the PROMs. Some patients showed up for testing at 1-2 years but did not complete the questionnaires. The last study visit is defined as the last of either the 1-2 years test day or completion of the 1-2 years PROMs.

STATISTICAL ANALYSIS PLAN for the Achilles trial

For analysis and tabulation purposes, we define study time points as

Time Point Label	Target Day	Definition (Day window)
TP1. Baseline	Day 0 (Randomisation)	Information up to randomisation + 14 days
TP2. Month 3	91	Days 61 to 121
TP3. Month 6	182	Days 151 to 212
TP4. Year 1-2	364	Days 334 to 728

3 Statistical Principles

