3.3 Analysis Populations

We define the following patient population in this trial.

- **All randomized patients:** All patients that have been randomized regardless if they actually received treatment or not.
- **Full analysis set (FAS):** All patients that are randomized, received treatment, and where ATRS was measured at least once post baseline (i.e. at 3 months, 6 months or 1-2 years). Patients are allocated to the treatment they were randomized to.
- **Per protocol set (PPS):** Similar to the FAS, but patients are allocated to the treatment they actually received.
- **Complete Case set (CCS):** The subset of patients in the FAS that has ATRS measurements at all follow-up visits. Patients are allocated to the treatment they were randomized to.

The FAS will be used for the primary analysis, while the PPS and the CCS will be used for sensitivity analyses.

4 Trial Population

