5.1.1.2 Achilles tendon Total Rupture Score

The acute Achilles tendon Total Rupture Score (ATRS) was developed in Sweden and published in 2007 (2). The ATRS is a patient reported outcome measure (PROM) designed to assess outcomes in patients with ruptures of the Achilles tendon. It contains ten questions, and each question is answered on an 11-point Likert scale ranging from 0 to 10. The total score is calculated by summing the individual Likert items. A score of 100 represents the absence of symptoms, whereas a score of 0 represents severe symptoms. The Norwegian version of the ATRS was validated, reliability tested and published in 2017/2018 (3). The Norwegian adaption of the ATRS demonstrates acceptable validity and reliability for use in the Norwegian population to assess clinical outcomes in patients with Achilles tendon ruptures.

If any of the 10 questions lacks an answer, this trial will follow the ATRS manual (8). Most importantly, if one or more of the 10 questions lacks an answer, the total ATRS score is treated as a missing value.

5.1.1.3 Short Form 36

STATISTICAL ANALYSIS PLAN for the Achilles trial

The Short Form 36 (SF-36) is a self-assessment health status questionnaire composed of 36 questions sorted into eight multi-item scales. The SF-36 also provides two summarized measures represented by the physical component summary (PCS) and the mental component summary (MCS). The validity and reliability of the Norwegian translation of SF-36 have been found to be satisfactory (4, 5).

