5.2.4.4 Missing Data

We expect three types of missing data for these outcome variables:

1. Individuals is present in the gym, tries to perform the test, but do not manage to fulfil the minimum requirements to have the test approved. These values are in reality censored rather than missing.
2. Value may be missing due to e.g. non-working equipment in the gym where the test takes place, even if the patient were physically there.
3. Values may be missing because the patient did not show up for the physical tests.

The following handling of the three types of missingness will be performed:

1. Threshold imputation: These values will be imputed in the following way:
 - I. The 1% highest and 1% lowest observed values for the variable will be removed, and a normal distribution will be fitted to the 'trimmed' observations.
 - II. Values "klarte ikke" (did not manage) will be replaced by drawing values from the distribution in point I, truncated by 0 and the 10th percentile of the distribution.
2. These values are assumed to be missing at random, and multiple imputation by chained equation will be performed.
3. Multiple imputation using chained equations will be used to impute these values.

The multiple imputation in point 2 and 3 will be done simultaneously, after point 1 has been performed. The following variables will be used to impute the test scores at 6 months and 1-2 years: Sex, Age, Weight at baseline, weight at the time of the test, study centre, results in the other 5 physical tests, results from all 6 physical test in the healthy foot, and ATRS scores at 6 and 1-2 years.

STATISTICAL ANALYSIS PLAN for the Achilles trial

Note that the LSI variables, which is the ratio between the injured and the healthy foot multiplied by 100, will not be imputed as described above. For the threshold imputation, the value in the injured and healthy foot will be imputed separately, and the LSI value is obtained from these. In the multiple imputation procedure, the LSI variables for the different tests will be imputed by passive imputation.

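### Patients with a physical-test result or scorable SF-36 but no complete follow-up ATRS at any visit are left out of those secondary comparisons, while never-tested FAS members are imputed into the physical-test ones

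*SAP*

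**What the plan says.** - **Analysis set.** SAP section 5.2.4.1 closes with "The analyses will be conducted in the FAS", and section 5.2.3.1 does the same for SF-36.
- **Entry to the FAS.** Section 3.3 requires randomisation, receipt of treatment, and that the patient is one "where ATRS was measured at least once post baseline". Any of the three follow-up visits will do.
- **What counts as an ATRS.** Section 5.1.1.2: "if one or more of the 10 questions lacks an answer, the total ATRS score is treated as a missing value". Section 5.2.1.4 repeats the rule visit by visit.
- **What counts as an SF-36.** Section 5.2.3.4 is more lenient: "Note that the manual allows for a certain degree of missingness in a given questionnaire".
- **Tests and questionnaires can come apart.** Section 2.7 reports both directions at 1-2 years: "Some patients showed up for testing at 1-2 years but did not complete the questionnaires", and "Some patients did not show up for the 1-2 years testing but did complete the PROMs".
- **Untested patients.** Section 5.2.4.4 lists as its third type of missing data: "Values may be missing because the patient did not show up for the physical tests". These values are multiply imputed by chained equations.
- **Sensitivity analysis.** Section 5.2.4.5 repeats the 5.2.4.1 analysis in patients who attended the test, after the threshold imputation. It does not say whether attenders outside the FAS are included.

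**The concern.** Entry to the analysis of one outcome depends on completing the form for another. For the primary analysis the ATRS condition has a purpose, because a patient with no follow-up ATRS contributes nothing to the mixed model for ATRS. For a heel-rise test or an SF-36 score it has none: the outcome may have been measured and be in the database, yet the patient is set aside.

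The treatment of the two kinds of incomplete patient is also uneven. A patient with a test result and no ATRS is out; a patient with an ATRS and no test result is in, by imputation. At stake are some precision and a possible selection effect in secondary outcomes. The wording of 5.2.4.5 also leaves room for two analysts to build different sets.

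**Working it through.** The plan gives no figure on this point to reproduce. The check is first a reading of the sections together, then an illustration of size.

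**1. Who is in and who is out.** All patients below are randomised and treated.

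| Patient | In FAS? | Result |
|---|---|---|
| Complete ATRS at 3 months only; tested later | Yes | Measured tests are used |
| Complete ATRS at 3 or 6 months; tested at 1-2 years without questionnaires | Yes | Measured tests are used |
| No complete ATRS at any follow-up visit; tested at least once | No | Measured tests are left out |
| No complete ATRS at any follow-up visit; scorable follow-up SF-36 | No | SF-36 is left out |
| At least one complete ATRS; never tested | Yes | Tests are imputed |

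The defect is confined to the third and fourth rows; the fifth supplies the contrast.

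**2. Endpoints governed by the rule.** Section 5.1.3.4 has 6 tests, each as a raw result and as a limb symmetry index, each at 6 months, at 1-2 years and as the change: 6 × 2 × 3 = 36, as the SAP states. SF-36 adds three scores (PCS, MCS, PF).

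**3. Does the imputation need the ATRS condition?** The chained equations in 5.2.4.4 use ATRS at 6 months and 1-2 years as predictors. A patient with a 3-month ATRS only is in the FAS and lacks both. The procedure must already cope with missing ATRS, so the condition has no technical purpose here.

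**4. How many patients could have no follow-up ATRS?** The only input from the SAP is the enrolment target of 530 (section 2.3), all taken as treated. Assume each follow-up ATRS is missing with probability m.

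- If visits are independent, the share of patients missing the 1-2 year ATRS who still qualify for the FAS is 1 − m².
- Patients with no ATRS at any visit: 530 × m³ if visits are independent; 530 × m if the same patients miss every visit.

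| m | 1 − m² | 530 × m³ | 530 × m |
|---|---|---|---|
| 10% | 99% | 0.5 | 53 |
| 20% | 96% | 4.2 | 106 |
| 30% | 91% | 14.3 | 159 |

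Independence is optimistic, because non-response tends to cluster in the same patients; the last column is the opposite extreme. These counts are patients without any ATRS, most of whom may never have been tested either.

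**5. How many of those were tested?** Let q be the share of the 530 with no complete follow-up ATRS, and t the share of those who attended a test. The number excluded despite a test is 530 × q × t.

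- Low: 530 × 0.01 × 0.10 = 0.5
- Middle: 530 × 0.03 × 0.30 = 4.8
- High: 530 × 0.05 × 0.50 = 13.2

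The high case is 0.05 × 0.50 = 2.5% of those enrolled, about 13.2 / 3 = 4.4 per arm if spread evenly. The values of q and t are assumptions.

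**The case against.** **Most patients who give up on questionnaires are kept.** A reader might infer that anyone who stops answering but still attends testing is dropped. Section 3.3 does not support that: one complete follow-up ATRS at any visit is enough. Nor are the patients described in section 2.7 shown to be excluded, since they are known to lack only the 1-2 year forms. Nothing in the SAP says that any tested patient lacks an ATRS at all three visits. This objection stands, and it limits the point to the narrow group above.

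**No measured value is replaced.** A reader might also infer that imputed values take the place of real ones. They do not. Imputing FAS members who did not attend is ordinary missing-data handling in a fixed, as-randomised set and is separate from the exclusion. The two rules are uneven, but neither causes the other.

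**The sensitivity analysis may already cover it.** Section 5.2.4.5 names attenders as its population and does not mention the FAS. Read plainly, it removes the imputed non-attenders and could include every attender. But it does so by running the 5.2.4.1 analysis, which is set in the FAS, and it does not settle which governs. This stands in part.

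**The SF-36 case is remote.** Section 5.1.3.1 says ATRS and SF-36 are presented together, and ATRS has three follow-up occasions against two for SF-36. Exclusion needs a scorable SF-36 alongside an absent or incomplete ATRS at all three. That is fair as to size. Still, 5.2.3.4 describes exclusion for want of follow-up measurements in a section on SF-36 scores, which does not match a set defined by ATRS.

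**One common FAS is conventional, and any rule based on attendance also selects after randomisation.** Both are true. The proposed rule adds measured data; it does not remove all selection.

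**Conclusion.** The point holds in its narrow form, as a minor improvement. A treated patient with a physical-test result or a scorable follow-up SF-36, but no complete ATRS at any of the three follow-up visits, is outside the main analysis of that outcome. Never-tested FAS members are brought into the physical-test comparison by imputation.

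The number is not given and is probably very small: about 0.5 to 13 tested patients of 530 if 1% to 5% have no follow-up ATRS and 10% to 50% of those attended a test. A reader might infer bias between arms. The document supports neither a direction nor a difference by arm, and it does not describe blinding. The primary endpoint and the sample size are unaffected, and section 2.4.1 classes all tests outside the primary hierarchy as supportive or exploratory.

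**What to change.** Drop the ATRS condition from the analysis sets for these outcomes:

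- **5.2.4.1, physical tests.** Analyse randomised and treated patients, as randomised, who are in the FAS or attended at least one test. Keep the imputation in 5.2.4.4, with missing ATRS handled within the chained equations.
- **5.2.3.1, SF-36.** Analyse randomised and treated patients, as randomised, with at least one scorable follow-up SF-36. Keep the rule in 5.2.3.4 that brings in multiple imputation when more than 5% have no follow-up measurement.
- **5.2.4.5.** State that all treated attenders are included, whether or not they are in the FAS.

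This is SAP wording only and uses data already collected. The cost is that denominators for secondary outcomes will differ slightly from the primary FAS, so each table should state its own.

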5.2.4.2 Summary Measures

The effect estimates will be the pairwise differences in the estimated marginal means (that is, mean difference adjusted for study centre) between the treatment groups, reported together with 95% confidence intervals.

5.2.4.3 Assumption Checks

Visual inspection of residual plots will be performed (qq-plots, histograms and residuals vs. fitted values). Substantial deviations from normality will be addressed by suitable transformations of the data.

5.2.4.4 Missing Data

We expect three types of missing data for these outcome variables:

1. Individuals is present in the gym, tries to perform the test, but do not manage to fulfil the minimum requirements to have the test approved. These values are in reality censored rather than missing.
2. Value may be missing due to e.g. non-working equipment in the gym where the test takes place, even if the patient were physically there.
3. Values may be missing because the patient did not show up for the physical tests.

The following handling of the three types of missingness will be performed:

1. Threshold imputation: These values will be imputed in the following way:
 - I. The 1% highest and 1% lowest observed values for the variable will be removed, and a normal distribution will be fitted to the 'trimmed' observations.
 - II. Values "klarte ikke" (did not manage) will be replaced by drawing values from the distribution in point I, truncated by 0 and the 10th percentile of the distribution.
2. These values are assumed to be missing at random, and multiple imputation by chained equation will be performed.
3. Multiple imputation using chained equations will be used to impute these values.

The multiple imputation in point 2 and 3 will be done simultaneously, after point 1 has been performed. The following variables will be used to impute the test scores at 6 months and 1-2 years: Sex, Age, Weight at baseline, weight at the time of the test, study centre, results in the other 5 physical tests, results from all 6 physical test in the healthy foot, and ATRS scores at 6 and 1-2 years.

STATISTICAL ANALYSIS PLAN for the Achilles trial

Note that the LSI variables, which is the ratio between the injured and the healthy foot multiplied by 100, will not be imputed as described above. For the threshold imputation, the value in the injured and healthy foot will be imputed separately, and the LSI value is obtained from these. In the multiple imputation procedure, the LSI variables for the different tests will be imputed by passive imputation.

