2.3 Sample size

The sample size was based on the primary endpoint of ATRS at 1-2 years. The calculation was based on a one-way ANOVA analysis, assuming a standard deviation of 20 in each treatment group. A total sample size (study completers) of 480 (160 in each group) was deemed necessary to achieve 80%

STATISTICAL ANALYSIS PLAN for the Achilles trial

power to detect a difference of ATRS of 7 between the groups in two-sided tests at 5% significance level. To compensate for withdrawals/loss to follow-up, a total enrolment of 530 patients was targeted.

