5.2.4.5 Sensitivity Analyses

Performing the analysis described in Section 5.2.4.1 on the population of patients that showed up for the physical test. I. e. after the threshold imputation described in Section 5.2.4.4 has been performed.

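### The 'did not manage' values appear to be drawn at random only once, so the physical-test estimates depend on the random seed more than they need to

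*SAP*

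**What the plan says.** SAP section 5.2.4.4 separates three kinds of missing physical-test result. The first is the patient who attends and tries but does not meet the minimum requirement. Of these values the SAP says: "These values are in reality censored rather than missing".

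They are filled in two steps. The top and bottom 1% of observed values are removed and "a normal distribution will be fitted to the 'trimmed' observations". The failed attempts "will be replaced by drawing values from the distribution in point I, truncated by 0 and the 10th percentile of the distribution".

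Multiple imputation is named only for the other two kinds, equipment failure and non-attendance. For non-attendance the text is: "Multiple imputation using chained equations will be used to impute these values". On the order of the steps it says: "The multiple imputation in point 2 and 3 will be done simultaneously, after point 1 has been performed".

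The sensitivity analysis in section 5.2.4.5 is restricted to patients who attended and uses the data "after the threshold imputation described in Section 5.2.4.4 has been performed". It mentions neither several copies nor pooling. The results are pairwise adjusted differences "between the treatment groups, reported together with 95% confidence intervals" (section 5.2.4.2).

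These sections do not say how often the threshold draw is made, how many imputations are used, or which seed is set.

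**The concern.** A random draw made once and then kept is one realisation out of many equally valid ones. On the natural reading of section 5.2.4.4, the same drawn values sit in every imputed dataset, so averaging over the imputations does not average them out. In section 5.2.4.5 nothing is averaged at all. An analyst who follows the SAP faithfully with another seed will report different estimates and interval limits from the same trial data.

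The draws also travel further. The other five test results are predictors in the chained equations, and the limb symmetry index is computed from the imputed feet. The SAP counts 36 physical-test endpoints (6 tests × 2 scales × 3 time comparisons). With three pairwise comparisons each, that makes 108 contrasts, so some are likely to be borderline. At stake is the reproducibility and, to a small degree, the precision of these secondary results.

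**Working it through.** **The plan's own figure.** The only design calculation is in section 2.3: "A total sample size (study completers) of 480 (160 in each group) was deemed necessary to achieve 80"% power. With SD 20, a two-sided 5% level and means spaced 0, 3.5 and 7 (the spacing is an assumption), the noncentrality of the one-way ANOVA is 160 × (3.5² + 0² + 3.5²)/20² = 9.8. Power is 80.4%, and 159 per group is the smallest size reaching 80%. The figure reproduces. It is used here only to take n = 160 per arm.

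**Assumed inputs.** The SAP gives no failure rates or spreads for the physical tests. The range used is 10–30% failures (f) and a coefficient of variation (CV, SD/mean of observed values) of 0.3–0.5. Observed values are normal with SD scaled to 1.

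**Formulas for a two-arm difference with n per arm.** Let τ² be the variance of the drawn values and δ the distance between the observed mean and the mean of the draws.
- Variance between seeds: B = 2fτ²/n.
- Variance of one completed arm: s² = (1−f)·1 + fτ² + f(1−f)δ².
- Squared standard error reported from one draw: W = 2s²/n.
- Seed-to-seed SD relative to the standard error: √(B/W) = √(fτ²/s²).

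**Worked example, CV 0.25, f = 0.20** (just outside the range, chosen because a simulation of the same case is available).
1. Observed mean 1/0.25 = 4. Trimming 1% at each end reduces the SD to √(1 − 2 × 2.326 × 0.02665/0.98) = 0.935.
2. Fitted 10th percentile: 4 − 1.2816 × 0.935 = 2.80.
3. A normal with mean 4 and SD 0.935, truncated to 0–2.80, has mean 2.36 (δ = 1.64) and variance τ² = 0.147.
4. s² = 0.80 + 0.20 × 0.147 + 0.16 × 1.64² = 1.260.
5. √B = √(2 × 0.20 × 0.147/160) = 0.019; √W = √(2 × 1.260/160) = 0.125; ratio 0.153.

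The simulated threshold step gave 0.019, 0.125 and 0.152.

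**Ends of the assumed range.**
- CV 0.5, f = 0.10: τ² = 0.047, s² = 1.109, ratio √(0.10 × 0.047/1.109) = 0.065.
- CV 0.3, f = 0.30: τ² = 0.141, s² = 1.305, ratio √(0.30 × 0.141/1.305) = 0.180.

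Simulation with three arms of 160 gave about 7–19%.

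**Can the seed change a conclusion?** In simulated datasets (100 or 160 per arm, CV 0.25–0.6, failures 5–40%), p-values over 100 seeds fell on both sides of 0.05 in 0–9% of datasets when failure rates were equal. With 20% against 30% failures the figure was 11–36%. These are crossings somewhere among 100 seeds, not the chance that one re-run changes the answer.

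**Are the single-draw intervals too narrow?** The term fτ² is part of s², so W contains 2fτ²/n, which is exactly B. The scatter of the independent draws is already in the residual variance. Simulation agrees:

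| Analysis | Reported SE / true sampling SD |
|---|---|
| Single draw | 0.98–1.02 |
| Repeated draws, Rubin's rules | 0.995–1.05 |

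Coverage of the estimator's own mean with a single draw was 94.8–95.5%.

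**Precision lost.** Repeated draws remove most of B. The true SD with one draw is about 0.3–1.6% larger than with repeated draws.

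**Not simulated:** study centre, the later chained equations, the limb symmetry index, and the change from 6 months to 1–2 years.

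**The case against.** The SAP nowhere says that the draw is made once. That is correct: it is an inference from the order of the steps and from section 5.2.4.5, which uses the threshold-imputed data with no pooling. If repetition was intended, one sentence settles it.

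A reader might infer more, namely that a single imputation leaves uncertainty out of the standard error and makes the intervals too narrow. Comparing √W with Rubin's √(W + B) seems to show this, with a shortfall of up to about 2%. But that compares two formulas, not a formula with the truth. Each failed attempt is drawn independently, so the draw noise is already in W. Error in the fitted mean and SD is shared by the arms if one distribution is fitted per variable, as the text suggests, and then largely cancels in a difference. The single-draw intervals are about nominal, and it is the pooled ones that become slightly conservative. This part of the objection stands in full.

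It is also fair to say that any finite number of imputations leaves some seed dependence, that section 2.4.1 makes all tests outside the ATRS hierarchy supportive or exploratory, and that section 5.2.4.2 plans intervals without a decision rule. These points limit the importance of the finding. They do not remove the noise, which is avoidable.

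**Conclusion.** The point holds as a matter of reproducibility and minor precision. Read naturally, sections 5.2.4.4 and 5.2.4.5 let the reported muscle-lab differences depend on one random draw. The resulting seed-to-seed SD is about 7–19% of the standard error, and the avoidable loss of precision is about 0.3–1.6%. Both figures rest on 160 per arm and on assumed failure rates of 10–30% and CVs of 0.3–0.5. With fewer failures or wider relative spread the effect is smaller.

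The plan does not support a claim of invalid or too-narrow confidence intervals. Near-nominal coverage here refers to the estimator's own mean; it does not show that the range from 0 to the 10th percentile is the right model for the censored values. The primary ATRS analysis is untouched. This is a desirable improvement, not a necessary correction.

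**What to change.** - **Section 5.2.4.4:** state that the threshold values are redrawn independently in each of the m imputed datasets before the chained equations are run, and that the results are pooled by Rubin's rules.
- **Section 5.2.4.5:** average over m threshold draws and pool in the same way.
- **Both sections:** fix m and the seed before the analysis.

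No new data are needed, and no endpoint or analysis model changes. One step moves inside the imputation loop, and the sensitivity analysis is run m times. The downside is that the pooled intervals become slightly conservative: the reported standard error is about 0.2–2% wider than from a single draw. Some seed dependence remains at any finite m, but it shrinks as m grows.
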